9.4 Data Sources

The reported data for the study will be available from the patient's file as well as the documentation done at the FPZ training center.

9.5 Study Size

Ciprian et al. (2013), Masiero et al. (2014) and Ygrit et al. (2013) show BASMI improvement of one point in populations receiving structured physiotherapy, compared to control groups (Liang et al. 2015). With the assumed detectable difference of one BASMI point, an assumed power of 80% and a standard deviation of 3.7 the sample size per arm is calculated to be 216 patients (total 432 patients).

Due to a complex enrolment flow, the long duration of the non-interventional study and the physical exposure of the patients we may expect a dropout rate of 15%, resulting in a total enrolment of 510 patients.

9.6 Data Management

Data for this study will be recorded in German by each participating center via an electronic data capture (EDC) system using a web-based eCRF with a unique subject ID code on a web-based encrypted platform. The participating site enters all data following pseudonymization. Data of clinical examination, diagnostic measures, laboratory assessments, findings and observations routinely performed in patients with humira® therapy included in this cohort, will be transcribed by hand by the rheumatologist or study nurse from the source documents into the eCRF. And the source documents will be stored on site. Only data specified in the protocol will be

entered into the eCRF. For each enrolled patient, the investigator or designee will create a new patient file in the eCRF and a unique patient number will be automatically allocated by the system. A comprehensive data validation program utilizing front-end checks in the eCRF will validate the data. Plausibility checks on defined limits and variable values will take place automatically. Automated checks for data consistency will be implemented; discrepancies need to be solved by the researcher in the eCRF before the module can be completed.

Follow-up on eCRF data for medical plausibility will be done by AbbVie medical personnel (or their representatives). Queries will be generated in the eCRF for online resolution at the site. The investigator or an authorized member of the investigator's staff will make any necessary data corrections to the eCRF. All change information, including the date and person performing the corrections, will be available via the audit trail, which is part of the EDC system. The principal investigator will finally review the eCRFs for completeness and accuracy of available data and provide his or her electronic signature and date to the eCRFs as evidence thereof. In addition, a qualified representative of the AbbVie medical department who is obliged to maintain confidentiality will visit the site periodically to conduct quality assurance measures. This includes training staff before study initiation, answering questions and clarifying any queries. Source data verification may be organized in collaboration with study personnel.

Access to the EDC system will be provided for the duration of the study through a password-protected method of internet access. Such access will be removed from investigator sites at the end of the site's participation in the study. Data from the EDC system will be archived on appropriate data media (e.g. CD-ROM) and provided to the investigator as a durable record of the site's eCRF data. Original Questionnaires will be sent from the participating site to:

e.factum GmbH
[name]
[name]

9.7 Data Analysis

9.7.1 Analysis populations:

Safety set: all patients enrolled and received at least one treatment with Humira®

ITT set: all patients randomized

Per protocol set (PPS): all patients randomized and performed AST or SOC physiotherapy until 6 months without severe protocol violations

Note: Several per protocol sets might be defined according coherence with AST and SOC treatment, respectively. Those specific PPS will be defined in SAP.

9.7.2 Background and demographic characteristics:

Continuously scaled variables will be described by mean, standard deviation, median, min, max, Q1 and Q3. Categorical variables will be described by counts and percentages.

9.7.3 Analysis of primary endpoint:

The primary analysis will be performed at ITT set.

The BASMI at 6 months (V5) will be analysed within an ANCOVA with treatment as fixed effect and baseline BASMI (V3) as covariate. The treatment effect will be reported with its 95%-confidence interval. In case prerequisites of ANCOVA are not given, according methods might be applied (transformation of data).

Note: The BASMI (BASMIlin) is continuously scaled, because it is the mean of 5 analog measures on a scale 0 - 10.

9.7.4 Analysis of secondary endpoints:

Continuously scaled variables with available baseline data will be analysed like the primary endpoint.

If baseline data are not available, 2-paired t-test will be applied.

The analysis of categorically scaled outcome variables by treatment will be performed by contingency tables. Related tests (χ^2 -Test, Armitage trend test) will be performed. Binary variables will be analysed by logistic regression.

All treatment related effects will be reported with their 95% confidence interval.

9.7.5 Missing data and sensitivity analyses

(1)

Missing data within questionnaires (single items are missing) will be imputed questionnaire specific rules. If such rules does not exist, missing single items will be replaced by the mean or median (details: see SAP) of the other items of the respective patient at the specific visit, if no more than 25% of the items are missing. If more than 25% of items are missing, the whole score is set to missing.

(2)

One might expect that patients finish either the AST or the SOC physiotherapy for several reasons.

In case of less than 10% of missing data for primary outcome variable, the complete case analysis is efficient. In case of more missing data, the following approaches will be applied in the sense of sensitivity analyses.

First, the underlying mechanism will be investigated by logistic regression modelling (missing information y/n = f(baseline data, success of treatment between enrollment and baseline assessment)). In case of MCAR (missing completely at random) the analysis will be performed at complete cases. In case of MAR (missing at random), multiple imputation might be applied in a sensitivity analysis. In case of MNAR

(missing not at random) a specific analysis is not possible, and scenario assuming several drop-out scenario will be investigated. Such sensitivity analyses (e. g. last observation carried forward, baseline value is carried forward, missing AST will be imputed by respective SOC data) will be defined in statistical analysis plan.

9.7.6 Assessment of covariates

Within primary model further influencing variables (baseline data, data describing success of treatment between enrollment and baseline assessment) might be investigated. Details will be provided in SAP.

Centers could be regarded as random effects within these models (mixed models) to investigate homogeneity of the effects.

9.7.7 Safety data

Safety data will be described using the safety set. The data will be presented by severity, intensity, requirement of treatment, system organ class, causality, outcome, action taken.

9.7.8 Data review and SAP

Data will be investigated in a blinded data review meeting in terms of protocol violations and missing data. Consequences for analysis will be taken into account in the SAP.

Complete and specific details of the final statistical analysis will be described and fully documented in the Statistical Analysis Plan (SAP). The SAP will be finalized prior to the database lock. Complete and specific details of the final statistical analysis will be described and fully documented in the Statistical Analysis Plan (SAP). The SAP will be finalized prior to the database lock.

A final study report will be written. This report will contain a description of the objectives of the study, the methodology of the study and its results and conclusions.

9.8 Quality Control

Prior to any study-related data being collected, patient authorization to use and/or disclose personal and/or health data will be obtained and will be reviewed and signed and dated by the patient and physician who administered the patient authorization. A copy of the signed patient authorization will be given to the patient and the original will be placed in the patient's medical record. A patient authorization for use/disclosure of data template will be provided.

Prior to the initiation of the study, rheumatologists and site personnel will be trained on the study and the FPZ concept (described in Annex 1). Training will include a detailed discussion of the protocol and study procedures (study design, patient flow, in- and exclusion criteria), patient reported outcomes (PRO) and procedure of data management (e.g. eCRF completion). FPZ personnel will be trained on medical background of axial spondyloarthritis, disease characteristics and peculiar features of patients' clinical condition in regards to physical exercise.

All data generated by the rheumatologist will be entered via the eCRF. All data generated by FPZ will be transferred to CRO and inserted into the respective patient eCRF. After entry of the data, computer logic checks will be run to check for inconsistent data.

9.9 Limitations of the Research Methods**9.10 Other Aspects****10.0 Protection of Human Subjects**

This PMOS will be run in compliance with local laws and regulations (§4 German Drug Law, AMG). Notification/submission to the responsible regulatory authorities, Ethics Committee (EC), Health Insurance bodies and Competent Authorities (CAs) will be done as required by local laws and regulations.

The investigator is responsible to ensure that written informed consent to use and/or disclose patients' pseudomized health data will be obtained prior to patient inclusion.

To maintain patient confidentiality, no demographic data that can identify the patient will be collected (e.g. initials, date of birth) - only the patient age will be collected. In order to protect patient identity, a unique number will be assigned to each patient and related study recording.

11.0 Management and Reporting of Complaints

A Complaint is any written, electronic, or oral communication that alleges deficiencies related to the physical characteristics, identity, quality, purity, potency, durability, reliability, safety, effectiveness, or performance of a product/device after it is released for distribution.

Complaints associated with any component of this investigational product must be reported to the Sponsor (Section 11.2.2). For adverse events, please refer to Sections 11.1.1 through 11.1.6. For product complaints, please refer to Section 11.2.

11.1 Medical Complaints

11.1.1 Adverse Event Definition and Serious Adverse Event Categories

An adverse event (AE) is defined as any untoward medical occurrence in a patient, which does not necessarily have a causal relationship with their treatment. An adverse event can therefore be any unfavorable and unintended sign (including an abnormal laboratory finding), symptom, or disease temporally associated with the use of a medicinal product, whether or not the event is considered causally related to the use of the product.

Such an event can result from use of the drug as stipulated in the labeling, as well as from accidental or intentional overdose, drug abuse, or drug withdrawal. Any worsening of a pre-existing condition or illness is considered an adverse event.

If an adverse event meets any of the following criteria, it is considered a serious adverse event (SAE):

Death of Patient:	An event that results in the death of a patient.
Life-Threatening:	An event that, in the opinion of the investigator, would have resulted in immediate fatality if medical intervention had not been taken. This does not include an event that would have been fatal if it had occurred in a more severe form.
Hospitalization:	An event that results in an admission to the hospital for any length of time. This does not include an emergency room visit or admission to an outpatient facility.
Prolongation of Hospitalization:	An event that occurs while the study patient is hospitalized and prolongs the patient's hospital stay.
Congenital Anomaly:	An anomaly detected at or after birth or any anomaly that results in fetal loss.
Persistent or Significant Disability/Incapacity:	An event that results in a condition that substantially interferes with the activities of daily living of a study patient. Disability is not intended to include experiences of relatively minor medical significance such as headache, nausea, vomiting, diarrhea, influenza, and accidental trauma (e.g., sprained ankle).
Important Medical Event Requiring Medical or Surgical Intervention to Prevent Serious Outcome:	An important medical event that may not be immediately life-threatening or result in death or hospitalization, but based on medical judgment may jeopardize the patient and may require medical or surgical intervention to prevent any of the outcomes listed above (i.e., death of patient, life threatening, hospitalization, prolongation of hospitalization, congenital anomaly, or persistent or significant disability/incapacity). Additionally, any elective or spontaneous abortion or stillbirth is considered an important medical event. Examples of such events include allergic bronchospasm requiring intensive treatment in an emergency room or at home, blood dyscrasias or convulsions that do not result in inpatient hospitalization, or the development of drug dependency or drug abuse.

11.1.2 Severity

The following definitions will be used to rate the severity for any adverse event being collected as an endpoint/data point in the study and for all serious adverse events.

Mild: The adverse event is transient and easily tolerated by the patient.

Moderate: The adverse event causes the patient discomfort and interrupts the patient's usual activities.

Severe: The adverse event causes considerable interference with the patient's usual activities and may be incapacitating or life threatening.

11.1.3 Relationship to Pharmaceutical Product

The following definitions will be used to assess the relationship of the adverse event to the use of product:

Reasonable Possibility An adverse event where there is evidence to suggest a causal relationship between the product and the adverse event.

No Reasonable Possibility An adverse event where there is no evidence to suggest a causal relationship between the product and the adverse event.

If no reasonable possibility of being related to product is given, an alternate etiology must be provided for the adverse event.

11.1.4 Serious Adverse Event Collection Period

Serious adverse and non-serious events will be reported to AbbVie from the time the physician obtains the patient's authorization to use and disclose information (or the patient's informed consent) until 30 days or 5 half-lives following the intake of the last dose of physician-prescribed treatment.

11.1.5 Serious Adverse Event Reporting

Product-related events including Adverse Reaction Reporting

This is an observational research study not designed to identify or quantify a safety hazard relating to humira®.

If a patient reports a product-related event (e.g. suspected adverse reaction or product complaint) to his/her healthcare professional during the data collection period or the healthcare professional identifies a product-related event, which is considered related to humira® or any other AbbVie authorized product, the event should be reported to AbbVie. Any product-related events considered to be related to a non-AbbVie product should be reported in accordance with local laws and regulations to the relevant Regulatory Authority and/or drug marketing authorisation holder.

Patient Reported Outcome (PRO) data are not considered a potential source of adverse reactions. However, participating sites should review the PRO data and if a possible product-related event (including a suspected adverse reaction) is noted, the HCP must determine whether the event is related to humira® and if so, it should be reported to AbbVie.

In the event of a serious adverse event, and additionally, any non-serious event of malignancy in patients 30 years of age and younger, whether related to study drug or not, the physician will:

- For events from patients using an AbbVie product - notify the AbbVie contact person identified below within 24 hours of the physician becoming aware of the event.
- For events from patients using a comparator product - notify the Marketing Application Holder (MAH) for the comparator product within 24 hours of the physician becoming aware of the event.

This protocol requires all SAEs and non-serious adverse events as outlined in protocol section 11.1.1 to be actively solicited.

The relevant AbbVie Pharmacovigilance contact details are specified below:

AbbVie Deutschland GmbH & Co. KG
Arzneimittelsicherheit (AMS) AbbVie Deutschland
[name]
[name]

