### **6.6 *Safety data***

Safety data are described on the basis of the safety population. The data are broken down by severity, intensity, required treatment, system organ class, causal relationship, treatment outcome, and action taken.

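### For non-serious adverse events, Protocol 11.1.4 and 11.1.5 are not reconciled, and harms of the randomised training have no structured causality question and no planned table by arm

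*Protocol*

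**What the plan says.** The protocol file holds two texts, one naming Humira and one saying adalimumab. Their safety sections are nearly the same.

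- **Definition (11.1.1).** An adverse event is "any untoward medical occurrence in a patient, which does not necessarily have a causal relationship with their treatment". Worsening of an existing condition counts.
- **Collection period (11.1.4).** "Serious adverse and non-serious events will be reported to AbbVie from the time the physician obtains the patient's authorization". No condition on cause is attached.
- **Solicitation (end of 11.1.5).** "This protocol requires all SAEs and non-serious adverse events as outlined in protocol section 11.1.1 to be actively solicited".
- **Product-related clause (start of 11.1.5).** It concerns an event "which is considered related to humira® or any other AbbVie authorized product, the event should be reported to AbbVie".
- **Patient-reported data (11.1.5).** If a possible product-related event is noticed there, the physician decides whether it is related to the drug and, if it is, reports it.
- **Causality (11.1.3).** "The following definitions will be used to assess the relationship of the adverse event to the use of product". There are two grades. If the drug is judged not to be a reasonable possibility, another cause must be named.
- **Analysis (SAP 6.6).** The safety data are to be broken down by severity, intensity, required treatment, "system organ class, causal relationship, treatment outcome, and action taken".

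**The concern.** Both arms take adalimumab, and what is randomised is AST against SOC physiotherapy (Protocol 4.0 and 8.0). A harm that differs between the arms is therefore most likely to come from the training. Non-serious musculoskeletal complaints are a plausible harm of machine-based exercise, and they belong to the class of events for which the reporting rules do not agree.

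Two things are at stake. A site that follows the narrower clauses may not report a non-serious training injury, and an event that was also never recorded cannot be recovered by later tabulation. And for events that are recorded, the causality breakdown in the report would describe the drug and say nothing structured about the intervention under comparison.

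**Working it through.** No arithmetic beyond a count applies, so the check sets the rules side by side for one test case: a non-serious back strain after a training session, in a patient who stays on adalimumab.

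| Rule | Place | Condition on cause | Reaches the test case? |
|---|---|---|---|
| Report serious and non-serious events | 11.1.4 | none | yes |
| Solicit all events | end of 11.1.5 | none | yes |
| AE/SAE item at each visit, V0 to V7 | 9.1, Tables 1 and 2 | none | yes, as a scheduled item |
| Report product-related events | start of 11.1.5 | judged related to the drug or another sponsor product | no, if judged due to training |
| Report events seen in patient-reported data | 11.1.5 | judged related to the drug | no, if judged due to training |
| Notify within 24 hours | 11.1.5 | none | no, serious events only (plus malignancy at age 30 or younger in the Humira text) |
| Report events that lead to treatment discontinuation | 9.2 | none | no, the drug is continued |

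**Scope.** Serious events are outside the conflict. The Humira text of 11.1.5 has them notified whether or not related to the drug, and the adalimumab text sets no relatedness condition either. Events that lead to treatment discontinuation are reported whatever the cause. That rule in 9.2 follows text about stopping the drug, so it does not clearly cover stopping the training because of an injury. What remains is the non-serious event without treatment discontinuation. Three rules reach it, two pass it by, and no sentence says which governs recording and which governs reporting to the sponsor. In the Humira text, explicit related-or-not wording is attached only to serious events and malignancy in younger patients, which invites the narrower reading for everything else.

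**Attribution.** There are two paths under 11.1.3:

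1. Drug judged not a reasonable possibility: another cause must be named, and training can be written in as free text.
2. Drug judged a reasonable possibility: no other cause is asked for, so a joint or competing role of training is not prompted.

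Neither path gives a graded answer about training, and SOC physiotherapy has no question of its own either.

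**Tables.** SAP section 7 lists 3.1.1.1 to 3.1.1.6 (6 tables) and 3.1.2.1 to 3.1.2.4 (4 tables), so 6 + 4 = 10. By title they cover number, visit, intensity, seriousness, outcome and action taken, the last four also by SOC and PT. I read these as system organ class and preferred term, although the SAP abbreviation list gives SOC only as standard of care.

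- By causal relationship: 0 of 10
- By required treatment: 0 of 10
- By treatment group: 0 of 10, whereas most table titles in parts 1 and 4 of the same list do name the treatment group

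SAP 6.6 promises the first two breakdowns. A split by arm is promised in neither Protocol 9.7.7 nor SAP 6.6.

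**The case against.** The best defence is that the rules form a general duty plus an additional one. The narrower clauses sit under a sub-heading on product-related events, say that such events should be reported, and never say that others should not be. They concern reporting to the sponsor, not entry in the eCRF. Adverse events are a scheduled item at every visit in both arms, and the adverse-event form is not among the documents, so what it captures cannot be judged. Safety is not among the objectives in 8.0, and the physical exposure mentioned in 9.5 is one of three reasons for the assumed 15% dropout and says nothing about event capture.

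Much of this stands, and it rules out three stronger readings that a reader might infer:

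- *Only drug-related events are solicited or reported.* The word only does not appear. Solicitation covers all events, and 11.1.4 has no condition on cause.
- *Training-caused events are removed at the sites before analysis.* The documents show that a site could follow the narrower clauses. They do not show that any would, or that the eCRF would omit the event.
- *An event can never be attributed to training.* The alternative-cause rule in 11.1.3 allows it when the drug is ruled out. Because arms are randomised and visits are the same, a comparison by arm could also attribute an excess to training without any individual rating.

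What the defence does not answer: the general-plus-additional reading is plausible but nowhere stated, and the solicit-all sentence stands under the same sub-heading as the narrower clauses, so the layout does not separate them. The alternative-cause entry is unstructured and has no listed table. The by-arm comparison, which is the better tool, is not planned. Listing 5.9 gives adverse events as a listing, not a summary by arm.

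**Conclusion.** The point holds within limits. The reporting rules are unreconciled for non-serious events that do not lead to treatment discontinuation. The graded causality question is about a drug common to both arms. The table list omits two breakdowns that SAP 6.6 promises, and any split by arm.

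The size in events cannot be given. The documents contain no adverse-event rates, and how the roughly 50 sites would read 11.1.5 is unknown. The countable part is 0 of 10 tables for each of causality, required treatment and treatment group, judged from table titles alone.

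This does not touch the primary BASMI analysis. It limits what the report can say about harms of the training, and it should be corrected because the correction is cheap. The conclusion assumes that the eCRF form, which is not shown, does not already hold a training-relationship field.

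**What to change.** 1. **Protocol 11.1.5, both texts.** Reconcile the passages: state that every AE and SAE is recorded in the eCRF whatever its suspected cause, including events noticed in patient-reported data, and that the product-related clauses govern only pharmacovigilance reporting to the sponsor.
2. **Protocol 11.1.3 and eCRF.** Add a second relationship question, to AST or SOC physiotherapy, with the same two grades. Ask it in both arms and for every event, including those where the drug is a reasonable possibility.
3. **SAP section 7.** Add adverse-event tables by randomised arm in the ITT set, by causal relationship (to the drug and to the training or physiotherapy), and by required treatment. The by-arm tables need the ITT set because the safety set includes enrolled patients who were never randomised. They should count events from randomisation at V3 onward, since collection starts at V0.

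**Cost.** A few sentences of protocol text, one eCRF field and a few tables. Sites will have more non-serious events to enter. The training rating is made by people who know the arm, so it is descriptive, and the by-arm comparison should carry the inference. Item 3 can be done in the SAP alone, but it cannot recover events that were not recorded.
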